8.2 Compensation

The method for compensation will be determined separately by each site, listed in the site's informed consent/assent form, and approved by the single IRB (the UNC-CH IRB).

If a subject is unable to go into the clinic to complete a follow-up study visit, the web-based CASI survey could be completed on their own. Site study staff will be notified when a subject has completed a CASI survey on their own and the compensation will be provided to the subject. Additional compensation will be provided for participants who are asked to return to clinic site for laboratory/clinical testing or asked to complete a self-administered VL test. Site study staff will determine the appropriate amount of compensation. Compensation can be provided in person, or sent to participants electronically or via mail, if allowed at the site.

8.3 Intervening on “Social Harms”

(Describe potential harms that may occur as a result of participating in the study, and what steps will be taken to reduce or counteract the negative effects. These measures can be preventive or reactive.)

We identified the following 6 items as possible risks to subjects and described how we plan on addressing those risks:

1. Protecting against going to the site by mistake. We have a secure site ([https:](https://)) with an introductory page clearly specifying the nature of the study. Sensitive survey or intervention content is protected behind screening questions and a username/password, and therefore in the opening study webpage, we could not think of anything that would be deemed offensive by any persons or those who might be vulnerable. In this way, we have minimized the risk to a level that is negligible.
2. Protecting against others finding out about their sexual behavior, sexual orientation identity, or HIV status. Participants will be alerted to this and provided basic information on how to best protect themselves. Specifically, those who qualify for the study will have access to an informational page describing how we protect their confidentiality and what steps participants can take to protect their confidentiality during the study. The description of the purpose of the study will clearly state that the study is designed so that participants are encouraged to interact with one another virtually, and we will recommend that persons who are highly uncomfortable with such exchanges may be better served by not enrolling in the study. Once enrolled, we also minimize this risk of identification to participants in the following ways: a) participants will be required to create usernames that do not contain personally identifying information and the site will be continuously monitored to maintain high levels of confidentiality and b) participants may utilize the features of the intervention that they choose, although we will encourage the exploration of all features. Thus, although we cannot guarantee their anonymity, we will take appropriate safeguards to minimize this risk.
3. Protecting against discomfort in answering personal questions during the focus group discussions, the assessments, and/or revealing aspects of themselves during the intervention period with other participants. This risk is similar to #2 above, and we will use comparable safeguards to protect against it. Thus, we intend to fully inform participants of the purpose and nature of the study prior to their participation. Participants in all of the protocols are informed that they are free not to answer questions or utilize study features, and they may stop participation at any time. Since a “refuse to answer” option is provided to every self-report question in the study surveys, there is a constant reminder of their participant rights throughout the study. Internet-based studies may be less invasive than conventional study methodologies, as it provides users total control over their participation and they may opt out of the study by simply exiting the study website. We believe the risk to participants is minimal and we have adequately anticipated and set into place protocols to address potential risks that may arise.
4. Protecting against hostile interactions and inaccurate information from one participant to another. Participants will be informed during the consent process of the “group rules” regarding interactions with one another (e.g., “Honesty is important; however, hostile or abusive language will not be tolerated and may be grounds for immediate removal from the study”). These “rules” will also be available with a link on all intervention web pages for review by participants at any time. The project coordinator will manually review an automated compilation of posts participants make on a daily basis to flag hostile interactions and inaccurate information. Hostile interactions between participants will be handled by, first, reminding the participants in the interaction of the “group rules” regarding appropriate interactions. If the hostility continues, the offending participants

will be given a warning that the continued hostility will result in withdrawal from the study if it continues. On the third offense, the offending participant will be withdrawn from the study. Text containing hostile exchanges will be removed from the study website and unavailable to view. In cases in which inaccurate information is found, project staff be guided by experts on the team to post a comment that provides accurate information on the topic. In extreme cases, the PI's may decide to withdraw a participant before the third offense. We will ensure all clinic sites have a clear clinical protocol to address major issues that may come up at study visits or in online interactions. The major issues addressed in the protocol will be suicidal ideation, homicidality or violent ideation, emotional and cognitive disregulation, violent/aggressive or disruptive behavior, and intoxication. If research staff from San Diego State University see concerning comments or messages online from participants regarding self-harm or harm of others, they will contact clinicians at the site and take immediate precautions.

5. Protecting against concerns about the security of their data. Well-established security protocols will be followed, that include the following:
 1. Participants' identifying information is kept separate from the data set, in a separate file on a separate computer in the offices of the PI's, accessible only by authorized study staff.
 2. All data will be encrypted and stored on a password-protected computer behind a firewall to ensure access is provided only to those involved directly in data collection or analysis.
 3. Payment to subjects will be administered by research staff during the baseline, and immediate post-intervention follow-up.
 4. At the end of the study, the identifying information (participants' names and contact information) is destroyed. The original data records will be archived for 7 years (in accord with good data practices), and three copies of the de-identified dataset will be maintained (a working one and two archived at different sites).
 5. All project staff will be required to complete the NIH online training in research ethics. Further training and supervision will focus research staff on confidentiality concerns both during and after the study. The project coordinator in conjunction with the PI are responsible for ensuring that all research staff involved in this study document their NIH training.
6. Minimizing the risk and discomfort from phlebotomy and VL testing. Trained and certified phlebotomists will perform all blood draws done in person in order to minimize the risk of bruising or infection. In order to minimize discomfort, an experienced and/or certified medical assistant will perform these procedures. They are routinely done in medical settings, and therefore potential risks are no greater than those encountered during routine medical exams. SRV staff will make every effort to align participants' data collection time points with standard clinic viral load measures. When these do not align, an additional blood draw or self-collected VL testing will be needed. For both standard VL testing and self-administered VL testing, physical harms are minimal. The type of safety lancet selected for use in the study was designed to minimize the potential for infection or significant injury. Cleaning the area with an alcohol pad first lowers the already low infection risk further; pads are included in every kit. The spring-loaded lancet retracts fully after one firing, and thus does not pose a risk for "needle stick" injury to anyone after the device has been used. Subjects could experience dizziness, diaphoresis and nausea associated with the procedure but in prior clinical studies using self-administered testing, adverse events have been rare.

All sites have specific policies governing the treatment of human subjects. These policies specify that medical and psychological assistance will be available in the immediate environment in the event a participant should experience any adverse reactions resulting from study procedures.

While participants will be informed that they may refuse to answer any question at any time, responses or reactions to certain questions may indicate distress on the part of the participants. If at any time during the study, a participant divulges that they are at risk for harm, including but not limited to being abused or experiencing violence, if harm is suspected or likely, or if the participant states they are suicidal/homicidal, measures will be taken to ensure their safety. Reporting will be done as appropriate to the situation and the legal statutes, including reporting to child protection agencies or other appropriate agencies, and referrals will be provided to appropriate support, counseling, or treatment resources.

8.4 Criteria for Premature Study Discontinuation

Subjects will be prematurely discontinued from the study if any of the following occurs:

- The subject withdraws consent/assent;
- The subject becomes incarcerated or placed in detention
- The participant is unwilling or unable to comply with study procedures
- The investigator believes that ongoing participation may cause harm to the participant or study staff
- The investigator believes that ongoing participation may impact the integrity of the study data
- The study is cancelled by the *NIH (or iTech, or other administrative entity)*;
- The study is cancelled for other administrative reasons;
- The subject becomes incarcerated or placed in detention during the study; or
- Death of the subject.

The *Study Stop CRF* will be completed when participants are study stopped. No medical record data on participants will be abstracted past the date of study discontinuation.

Subjects who are prematurely discontinued from the study may be allowed to re-enroll into the study on a case-by-case basis. The Protocol Team will review the number of slots opened for replacements on a monthly basis, or more frequently, as needed.

MONITORING UNTOWARD EFFECTS ASSOCIATED WITH OR RESULTING FROM STUDY

Site research staff must first follow their own IRB's procedure for reporting and managing untoward effects.

There are three types of untoward effects to be identified: (1) those related to the participant, (2) those related to the study staff, and (3) those related to the neighborhood/community (*if applicable*).

First, the study will catalogue any untoward effect related to the participant. Reporting is required for occurrences including social harms, psychological distress, and serious life-threatening events such as suicide attempts. These may be immediately apparent to the study staff, such as the participant's emotional upset state requiring referral for counseling; or they may be delayed and reported later to study staff, such as physical harm to an individual for having participated in the study. Study staff will notify the iTech team of any untoward effects using the iTech QNS accessible through the iTech website (www.itechnetwork.org) within 24 hours of becoming aware of these untoward effects. Study staff will be briefed during the training on the scope of possible untoward effects and instructed to report events.

Second, study staff may encounter untoward events during sessions that personally affect them. Training and guidance will seek to minimize this risk. Nonetheless, an assessment of the cost of conducting this study must include cataloguing these events as well. The protocol chairs should be notified of these events so that they may be immediately addressed, evaluated, and guidance modified or expanded to minimize similar risk to other study staff.

Third, a critically important area any community-based study intends to evaluate is the impact, including untoward effects, of the project on the community. This will be done informally for this protocol with untoward events being reported to the protocol team.

All untoward effects/adverse events/unanticipated problems will also need to be reported to the UNC IRB if they meet all three of the following criteria:

“Unanticipated problems involving risks to subjects or others” (UPIRSO) refers to any incident, experience, or outcome that:

- 1) is unexpected (in terms of nature, severity, or frequency) given (a) the research procedures that are described in the protocol-related documents, such as the IRB-approved research protocol and informed consent document; and (b) the characteristics of the subject population being studied;
- 2) is related or possibly related to a subject’s participation in the research; and
- 3) suggests that the research places subjects or others at a greater risk of harm (including physical, psychological, economic, or social harm) than was previously known or recognized.

Events that meet the criteria for an UPIRSO and are also serious adverse events should be reported to the UNC IRB within one (1) week of the investigator becoming aware of the event. Any other events that meet the criteria for a UPIRSO should be reported to the IRB within two (2) weeks of the investigator becoming aware of the problem.

If the report cannot be completed in its entirety within the required time period, a preliminary report should be submitted. The report should be amended once the event is resolved and/or more information becomes available.

STATISTICAL/ANALYTIC CONSIDERATIONS

10.1 Introduction

10.1.1 Focus Groups Overview

We will conduct six focus groups with approximately 8 youth (15-19 years old) and young adults (20-24 years old) each at 3 SRVs (Chicago, Houston, and New York) to obtain: 1) information about barriers to ART adherence and other challenges of living with HIV; 2) feedback from YLWH about the “look and feel” and content of the original *TWM* intervention; 3) suggestions for adapting the intervention for youth/young adults similar to themselves. Focus groups (as opposed to in-depth quantitative interviews) were chosen to gain feedback in these areas because this setting will allow participants to explore together the ways in which the *TWM* intervention meets their needs and how the intervention can be adapted to be community appropriate.

10.1.2 Usability Testing

A total of 12-20 YLWH across 6 SRVs (Bronx, Chicago, Houston, Philadelphia, Tampa, and Atlanta) will be recruited to provide feedback on the first full version of the *YT* intervention.

Usability testing is done to identify any technical problems with the program and any design features that are likely to impede engagement with the program.

10.1.3 RCT Overview

We propose to evaluate the *YT* intervention in a randomized controlled efficacy trial of 300 YLWH at 8 SRVs. YLWH will be recruited from the 8 SRVs, screened, and randomized to receive either the *YT* intervention or HIV-information only control condition. VL testing will be assessed at the enrollment visit and immediate post-intervention (5-month follow-up). We will evaluate interviews with up to 20 active users to obtain: 1) information about barriers to ART adherence and other challenges of living with HIV; 2) feedback from YLWH about the YouTHrive intervention; 3) suggestions for adapting potential future iterations of the intervention.

10.2 Power Estimates

10.2.1 Focus Groups Power Considerations

The purpose of focus groups is not to obtain generalizable data, but rather to obtain collective qualitative information to inform adaptation of the *TWM* intervention for youth. We are balancing feasibility with the need to obtain information from a spectrum of YLWH. As such, we will conduct 6 focus groups, targeting younger (15-19) and older youth (20-24) at 3 different SRVs with the goal of reaching 48 YLWH. Given our prior experience and best practices for the conduct of focus groups, this will provide us with information from enough youth to inform the adaptation process.

10.2.2. Usability Testing Power Considerations

Power is not a concern for usability testing as it is performed to collect feedback from a small number of members from the target population about a preliminary version of the intervention.

10.2.3 RCT of YT Power Considerations

We will continue to collect as much biologic data on viral load at baseline and month 5; however, given the difficulty in obtaining viral load measurements due to COVID, we will also utilize measures contained within our surveys to assess the impact of the intervention on self-reported HIV care continuum outcomes and possible mediating (social support) and moderating (depression) factors. We are already collecting this data, and thus will not need to modify our measures. We have been in discussions with SRVs about how many participants per month they believe that they could enroll. On average, sites reported that they would be able to recruit 4 participants per month each. If we begin the new inclusion criteria in April, then sites could potentially recruit up to 288 additional participants by The study statistician ([name]) conducted a power analysis to ensure our proposed changes will still allow for meaningful detection of primary study outcomes. Assuming approximately 85% follow-up, we based our updated power calculations on 240 participants. The primary outcome, self-reported adherence is a continuous measure. A study by Belzer et al. suggest a standard deviation of 43; assuming a type 1 error of 5% and equal allocation of participants between the 2 arms, we have 80% power to detect a difference of 15.6 points between the two groups. For instance, if the control arm had an adherence of 48% (as seen in Belzer et al.), we could detect a significant difference of 63.6% adherence in the intervention arm. This is a clinically meaningful difference. We have also assessed the impact of these proposed study changes on important secondary outcomes that have been shown to impact ART adherence among YLH (including depression

and social support). Based on a literature review, depression is estimated to have a prevalence between 25% and 40% in this population. Using the same assumptions as above, we have 80% power to detect a difference of 13.9% (if the prevalence is as low as 25% in the control arm) or 16.7% (if the prevalence is as high as 40% in the control arm). We are also assessing social support as measured by the PROMIS-ES scale. A study by Shensa et al allows estimation of a standard deviation of 0.63 for this score, giving us 80% power to detect a difference of 0.23 units. For example, if the control arm indicates a mean social support of 4, we could detect a difference if the intervention arm had a social support scale of 4.23.

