1.1 Background

Fifty thousand persons are estimated to be infected with HIV in the United States each year,¹ of whom one-quarter were youth between the ages of 13 and 24 years in 2010.² Young gay and bisexual men accounted for 72% of all new HIV infections in the same year, with the majority of those being black youth.² Despite elevated risk for HIV infection, it is estimated that only 6-16% of youth/young adults living with HIV (YLWH) are virally suppressed.³⁻⁵ Sufficient and sustained adherence to antiretroviral therapy (ART) reduces excess morbidity and mortality among people living with HIV (PLWH)⁶ and lowers the probability of forward transmission to sexual partners.⁷ Advancing targeted and innovative ART adherence interventions for YLWH is an urgent priority.³

Technology-supported ART adherence interventions have proliferated in recent years⁸⁻¹⁰ due to the widespread adoption of technology across sociodemographic groups,¹¹ their ability to reach a broad audience, rapid scalability, and low implementation costs.^{12,13} In the US, nearly all teens (between 12-17 years of age) use the Internet¹⁴ and 78% own a cell phone.¹⁵ Smartphone ownership among 18-29 year olds is high (86%).¹⁶ ART adherence interventions that leverage software on PCs or through the internet¹⁰ capitalize on consistency in delivery of content and long-term cost savings; however, to date the peer-to-peer interactivity that has come to symbolize Web 2.0¹⁷ remains underutilized in technology-based ART adherence approaches. Peer-to-peer support is a recommended strategy to improve ART adherence,¹⁸ is widely used by PLWH,¹⁹ and has an evidence-base for in-person approaches (especially with adults²⁰). However, youth in the US are increasingly accustomed to technology-mediated peer-to-peer interactions, suggesting that intervention approaches that specifically leverage high-use channels of interpersonal communication and support are needed.

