The “Thrive with Me” (*TWM*) intervention leverages enhanced peer-to-peer interaction, ART adherence reminders and self-monitoring, and ART and HIV informational content²¹ to improve ART adherence. In a pilot study of 123 adult MSM (average age = 43 years), those randomized to the *TWM* intervention showed improvements across all ART adherence outcomes compared to control participants, with greatest benefits for current drug-using MSM. Currently, our research team is funded to conduct an efficacy trial of an extended (5-month intervention period) and enhanced (tailored informational content; multi-dimensional self-monitoring; and gamification components, such as leveling and badges) version of the *TWM* intervention for adult MSM. Given youth’s broad acceptance and adoption of many of the components of the *TWM* intervention, and the critical need for novel and scalable ART adherence interventions for this population, the next logical step is to adapt the *TWM* intervention for YLWH.

As part of the UNC/Emory Center for Innovative Technology (iTech), we propose to test the efficacy of an adapted version of the *TWM* intervention, called YouT^Hrive (YT), for YLWH. In this 4-year study, 300 YLWH between the ages of 15-24 with detectable viral load (VL) will be randomized to the YT or an HIV information-only control intervention for a 5-month period. A target of 50% of YLWH participants with self-reported alcohol and/or illicit drug use will be enrolled. The primary endpoint is VL post-intervention.

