2.3 Study Hypotheses/Research Questions

- *H1: A higher proportion of participants in the YT intervention arm than in the information-only control arm will have undetectable VL at the 5-month follow-up time point.*
- *H2: Among YLWH in the YT intervention arm, a higher proportion of substance-using YLWH will demonstrate VL suppression at the 5-month follow-up time point compared to non-substance-using YLWH.*

STUDY DESIGN

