10.3.3 Primary Analyses for RCT of YouTHrive

Stata version 15 (StataCorp) and SAS version 9.4 (SAS Institute) were used for power calculations and will be used for all analyses. The primary study outcome is HIV viral suppression at 5 months, measured as undetectable VL based on the standard level of detectability. The primary statistical test of intervention efficacy for YT will be the comparison between intervention and control arms of the proportion of participants with undetectable VLs at the 5-month follow-up, using a chi-square test. If there is evidence of baseline imbalance between intervention arms for important predictors of viral suppression, we will fit logistic regression models that adjust for those covariates.

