Finally, we will examine models that include covariates that quantify the degree of site usage and which components were used. The additional outcome of self-reported ART adherence will be examined. The outcome will be defined as the percentage of ART taken in the past 30 days. Differences in this proportion by study arm will be evaluated using the same approach as described above. To explore the effects of the YT intervention on the intermediate theory-based processes of change, we will use the IMB-AAQ informational and motivational scales, adherence self-efficacy, and social support measures at each time point. These scales will be included as outcome variables in linear regression models to test the main effect of intervention arm.

Note: Any deviations from the analysis plans outlined above or in the sections that follow will be documented and justified in the Statistical Analysis Plan developed for this protocol.

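### The power section makes self-reported adherence the primary outcome, the analysis section makes undetectable viral load primary, and no power is given for the viral load test

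*Combined protocol and SAP*

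**What the plan says.** - **Section 10.2.3 (RCT power)** says "The primary outcome, self-reported adherence is a continuous measure". It assumes a standard deviation of 43, 240 participants in two equal arms and a 5% type I error, and reports 80% power for a difference of 15.6 points. Depression and social support follow, labelled as secondary outcomes, each with its own detectable difference.
- **Section 1.1** says "The primary endpoint is VL post-intervention".
- **Section 1.2.3** says that VL is measured in order to test the primary hypotheses.
- **Section 2.3, H1** predicts that a higher proportion of the YT arm than of the control arm "will have undetectable VL at the 5-month follow-up time point". H1 does not itself use the word primary; sections 1.1, 1.2.3 and 10.3.3 supply it.
- **Section 10.3.3** says "The primary study outcome is HIV viral suppression at 5 months, measured as undetectable VL based on the standard level of detectability" and names a chi-square comparison of proportions as the primary test.
- **Section 10.3.4**, under secondary analyses, says "The additional outcome of self-reported ART adherence will be examined". For the percentage of doses taken it adds "Differences in this proportion by study arm will be evaluated using the same approach as described above".

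No section gives a control-arm suppression rate for the trial, a target VL difference or an expected number of 5-month VL results.

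**The concern.** The primary outcome decides which result answers the trial's question. Here the power section and the analysis section name different ones, and both are current text. If VL and adherence disagree at 5 months, either could be reported as the prespecified primary result, with a passage to support it.

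The second problem is the power statement. A reader of 10.2.3 would take the 80% as the power of the trial's primary test. It is the power of a comparison of mean adherence. The chi-square test on VL has a different variance, which depends on a control rate that the plan does not state, and a different number of usable results, because 10.2.3 itself says that VL has been difficult to obtain.

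**Working it through.** **Step 1. Reproduce the plan's figure.** Inputs from 10.2.3: 240 participants, so n = 120 per arm; SD 43; alpha 5% (two-sided assumed, since it reproduces the figure); power 80%.

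δ = (z₀.₉₇₅ + z₀.₈₀) × SD × √(2/n) = (1.9600 + 0.8416) × 43 × √(2/120) = 2.8016 × 5.551 = 15.55 points.

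The noncentral t gives 15.62. Power at 15.6 points is 80.2% (normal) or 79.9% (t). The stated 15.6 is correct for a difference in means. A one-sided test would give 13.8.

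**Step 2. Check the two-proportion method on the plan's own figures.** The detectable difference δ solves

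δ = 1.960 √[2p̄(1−p̄)/n] + 0.842 √{[p_C(1−p_C) + p_T(1−p_T)]/n}, where p_T is p_C plus or minus δ and p̄ is their mean.

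For depression, as a reduction with n = 120, this gives 13.85 points from 25% (plan: 13.9) and 16.74 from 40% (plan: 16.7). The method matches the one behind 10.2.3.

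**Step 3. Apply it to the VL test.** The plan gives no control rate for the trial. Its only suppression figure is in the background: "it is estimated that only 6-16% of youth/young adults living with HIV (YLWH) are virally suppressed". Section 1.1 describes the randomised participants as having detectable VL, but the Aim 3 criteria in section 4.1 contain no VL requirement. The control rates below are therefore assumptions, and so is the column with 75 results per arm.

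Worked example at 50%: δ = 0.177 gives p̄ = 0.5885, and the right-hand side is 0.1245 + 0.0526 = 0.177.

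| Assumed control rate | Detectable increase, 120 per arm | Power for +15.6 points, 120 per arm | Detectable increase, 75 per arm |
|---|---|---|---|
| 6% | 11.6 | 94% | 15.7 |
| 16% | 15.3 | 81% | 19.9 |
| 30% | 17.5 | 71% | 22.3 |
| 40% | 18.0 | 68% | 22.7 |
| 50% | 17.7 | 69% | 22.1 |
| 60% | 16.7 | 74% | 20.7 |
| 70% | 15.0 | 83% | 18.4 |
| 80% | 12.4 | 96% | 15.0 |

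Detectable increases are in percentage points at 80% power, two-sided 5%, without continuity correction. Exact enumeration of the chi-square test at the 120-per-arm differences for control rates of 16% to 80% gives power of 0.79 to 0.81.

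**Step 4. Compare.** With all 240 VL results, the detectable VL difference is below 15.6 points at control rates of 6%, 16%, 70% and 80%, and above it from 30% to 60%. The adherence figure cannot stand in for it in either direction.

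**The case against.** The strongest reply is that one sentence in a power section does not outweigh the rest of the document. The objectives, sections 1.1 and 1.2.3, H1 and 10.3.3 all point to VL, and 10.3.3 fixes the outcome, time point and test. Section 10.2.3 also says that survey measures will be used in addition to VL, so the label may be a slip. This has force: the analysis section taken alone is not ambiguous.

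It does not dispose of the point, because 10.2.3 can also be read as a deliberate change. It gives a motive (VL hard to obtain), refers to new inclusion criteria and updated power calculations, and ranks depression and social support as secondary beneath adherence. It also speaks of primary outcomes in the plural, which may be loose wording or may mean co-primaries. The text does not settle which reading was intended, so the sponsor has to say. Under any reading, the VL test has no stated power.

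A second fair reply is that missing power is not low power. That stands. At low or high control rates with complete VL data, the detectable difference is smaller than for adherence.

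The wording on how adherence is analysed in 10.3.4 is a lesser matter. The approach it points back to covers chi-square, logistic, log-linear and Poisson methods, whereas 10.2.3 powered adherence as a mean. This needs clarification and is not a contradiction of the same weight.

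**Conclusion.** The concern holds and should be corrected before the analysis. The document names two different primary outcomes, and its 80% power belongs to the one that its analysis plan calls additional. The arithmetic behind the 15.6 points is sound.

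For the VL test with 120 results per arm, the detectable increase is 11.6 to 18.0 points over control rates of 6% to 80%. A gain of 15.6 points would have about 68% to 74% power at control rates of 30% to 60%. With 75 results per arm, the detectable increase would be about 22 to 23 points at control rates of 30% to 50%. The control rates and the 75 per arm are assumptions. The conclusion is that adequate power for VL is not shown; it is not that the trial is underpowered.

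**What to change.** 1. The sponsor should state which outcome is primary and make every section agree.
   - **If VL:** this is the smallest change. In 10.2.3, relabel self-reported adherence as a secondary outcome, and keep undetectable VL at 5 months as the single primary test at two-sided 5%.
   - **If adherence:** change the abstract objective and sections 1.1, 1.2.3, 2.1, 2.3, 10.3.3 and 10.3.4 instead, and give the reason for the switch.
   - **If both were meant as co-primaries:** say so and add a multiplicity rule.
2. If VL is primary, or one of two co-primaries, add to 10.2.3 the expected control suppression rate, the expected number of 5-month VL results, and the detectable difference for the chi-square test over a range of control rates. Include rows for fewer than 120 results per arm. The table above can serve as a start. With co-primaries, recompute it at the alpha level that the multiplicity rule sets.
3. In 10.3.4, state that percentage adherence is compared as a continuous outcome, for example by the linear regression already planned there for the scales.

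The cost is wording and one short table. No participants, visits or measures are added.
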